#### 5. ANALYSIS SETS

#### 5.1 All Randomized Set (ARS)

The ARS will include every participant randomized.

All analyses using the ARS will group participants according to the assigned treatment.

#### 5.2 As-Treated Set (ATS)

The ATS will consist of all participants who received any study treatment. All analyses using the ATS will group participants according to the actual treatment received.

If a participant is randomized to any dose level of AL002 and receives any amount of AL002, they will be analyzed at the highest dose level of AL002 received by the participant. Especially for participants who went on the dose titration algorithm (Table 3-1), their actual treatment received will be determined based on their Exposure – IV electronic CRF records and the participant visit dispensing history in the Interactive Response Technology (IRT) system.

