#### 3.1.4 Treatment Administered

All participants in Part 1 and Part 2 will receive study treatment (placebo, 15 mg/kg AL002, 40 mg/kg AL002, or 60 mg/kg AL002). Study drug administration will begin on Day 1 visit and then will occur once every 4 weeks for the duration of the treatment period according to the Schedules of Assessments in the protocol.

In order to maintain the blind across all dose groups and allow step titration to the higher doses, the starting dose for each participant randomized to receive AL002 will be 15 mg/kg (or placebo) for the first study drug administration on Day 1 visit. For the second study drug administration, the dose will increase to 40 mg/kg for participants randomized to receive 40 mg/kg or 60 mg/kg, while doses in the other 2 groups will remain constant. For the third study drug administration, the dose will increase to 60 mg/kg for participants randomized to receive 60 mg/kg while doses in the other 3 groups will remain constant. The titration algorithm is provided in below Table 3-1.

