#### 5.3.3 Non-e4/e4 Set

The Non-e4/e4 Set will consist of all participants who received any study treatment and are non-e4/e4.

All analyses using the Non-e4/e4 Set will group participants according to the actual treatment received and follow the same rules as described above in the ATS (Section 5.2).

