#### **6.3.2.1** Treatment-Emergent Adverse Events

- If both the start time of the AE and the time of the first study drug administration are available, an AE is considered a TEAE if its start date and time are after the first study drug administration start time and no later than 90 days after the last dose date. The last dose date is defined in Section 7.1.1.1.
- If either the start time of the AE or the time of the first study drug administration is unavailable, an AE is considered a TEAE if its start date is on or after the first dose date and no later than 90 days after the last dose date. Handling of incomplete dates is specified in Section 6.3.2.6.

Protocol No. AL002-2 Last Revision Date: 12 Aug 2025

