## 7.2 Participant Disposition and Protocol Deviations

#### 7.2.1 Participant Enrollment and Disposition

The number of participants screened, the number (percent) of participants who failed screening, and the reasons for screen failure will be summarized. A summary of participant enrollment will be provided by treatment group, AL002 40 and 60 mg/kg combined group, total AL002 group, and overall for each country, as well as for each investigator within a country. The summary will present the number and percentage of participants enrolled. For each column, the denominator for the percentage calculation will be the total number of participants analyzed for that column.

The randomization schedule used for the study will be listed.

A summary of participant disposition will be provided by treatment group, AL002 40 and 60 mg/kg combined group, total AL002 group, and overall. This summary will group participants according to the assigned treatment for all analysis sets. This summary will present the number of participants screened, the number of participants randomized, and the number of participants in each of the categories listed below:

- ARS
  - Randomized but never dosed
- ATS
  - Completed study drug
  - o Discontinued study drug
  - o Reasons for premature discontinuation of study drug
  - Completed study
    - Rolled over into LTE
    - Did not roll over into LTE
  - Discontinued study
  - Reasons for premature discontinuation of study
- Non-e4/e4 Set
  - Completed study drug
  - Discontinued study drug
  - o Reasons for premature discontinuation of study drug
  - Completed study
    - Rolled over into LTE
    - Did not roll over into LTE
  - o Discontinued study
  - Reasons for premature discontinuation of study
- e4/e4 Set
  - Completed study drug
  - o Discontinued study drug
  - o Reasons for premature discontinuation of study drug
  - o Completed study
    - Rolled over into LTE
    - Did not roll over into LTE
  - Reasons for premature discontinuation of study

Protocol No. AL002-2 Last Revision Date: 12 Aug 2025

For the status of study drug and study completion and reasons for premature discontinuation, the number and percentage of participants in each category will be provided. The denominator for the percentage calculation for the study drug completion/discontinuation and study completion/discontinuation will be the total number of participants in the corresponding analysis set.

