## 7.3 Demographics and Baseline Characteristics

#### 7.3.1 Demographics, Baseline Characteristics, and Medical History

Demographics, baseline characteristics, social history, medical history, and medical and surgical treatment procedures will be summarized by treatment group, AL002 40 and 60 mg/kg combined group, total AL002 group, and overall. Demographics and baseline characteristics will be summarized for the ARS, FAS, and the Non-e4/e4 Set, respectively. Social history, medical history, and medical and surgical treatment procedures will be summarized for the ARS and the Non-e4/e4 Set, respectively. By-participant data listings will be presented for the ARS.

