## 7.5 Safety Analyses

Unless otherwise specified, all safety data will be summarized by treatment group, AL002 40 and 60 mg/kg combined group, and total AL002 group, primarily for the Non-e4/e4 Set. Some safety data may be summarized for the ATS.

Treatment period and analysis visit window definitions are described in Section 7.1.1.2.2.

In the case of multiple values in an analysis visit window and a single value may be required for each analysis visit window (e.g., CFB by visit usually requires a single value), data will be selected for analysis as described in Section 7.1.3.2, unless otherwise specified.

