APOE genotype, time to the first occurrence, resolution, time to resolution, and reoccurrence will be summarized for participants with ARIA-E. APOE genotype and time to the first occurrence will be summarized for participants with post-baseline new ARIA-H.

The number and percentage of participants who had a post-baseline ARIA-E but did not have a new ARIA-H any time post-baseline will be summarized. The number and percentage of participants who had a new ARIA-H but did not have an ARIA-E any time post-baseline will be summarized. Similarly, the number and percentage of participants who had a new ARIA-H and an ARIA-E any time post-baseline will be summarized.

All the MRI summaries described above will also be provided separately for participants with the following APOE genotype(s) (1) e4/e4, (2) e4 carriers (including e2/e4, e3/e4 and e4/e4), (3) non-e4 carriers (excluding e2/e4, e3/e4 and e4/e4), and (4) e4 heterozygous carriers (including e2/e4 and e3/e4).

The Kaplan-Meier curve for the time to the first occurrence of ARIA-E will be plotted. For participants experienced at least one ARIA-E, the time to the first occurrence of ARIA-E is the time from the first dose date to the onset date of the first ARIA-E occurrence. For participants who did not experience ARIA-E, the censor date will be the earlier date of the last MRI scan date and the last dose date plus 90 days. Similarly, the Kaplan-Meier curve for the time to the first occurrence of new ARIA-H will be plotted.

All MRI findings will be listed.

Protocol No. AL002-2 Last Revision Date: 12 Aug 2025

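### Grouping safety data by highest AL002 dose received lets ARIA found during titration choose its own dose column, which distorts ARIA by dose

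*SAP*

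**What the plan says.** **Grouping.** SAP 5.2 (As-Treated Set) states that AL002 participants are placed so that "they will be analyzed at the highest dose level of AL002 received by the participant". It singles out titrated participants and takes their actual treatment from the exposure records and the dispensing history. SAP 5.3.3 repeats the rule: "All analyses using the Non-e4/e4 Set will group participants according to the actual treatment received and follow the same rules". SAP 7.5 then reports safety by treatment group, "AL002 40 and 60 mg/kg combined group, and total AL002 group, primarily for the Non-e4/e4 Set".

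**ARIA displays.** SAP 7.5.7 plans ARIA-E and ARIA-H incidence by visit and overall, and adds that "The Kaplan-Meier curve for the time to the first occurrence of ARIA-E will be plotted", with a matching curve for ARIA-H. Time runs from the first dose.

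**Titration.** In SAP Table 3-1 both higher arms get 15 mg/kg at Dose 1 and 40 mg/kg at Dose 2. The 60 mg/kg arm gets 60 mg/kg at Dose 3. Protocol 3.1.3 limits this to participants randomised after July 2021.

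**MRI and response to ARIA.** Protocol 7.11.1.1 schedules scans shortly before Doses 2, 3 and 4, and a footnote to protocol Table 9 requires the central result before dosing. Each row of protocol Table 7 either ends treatment or suspends it, with any restart held at the pre-ARIA dose from then on.

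**Assigned treatment.** Disposition is by assigned arm: "This summary will group participants according to the assigned treatment for all analysis sets". Baseline tables cover an assigned-arm set too: "Demographics and baseline characteristics will be summarized for the ARS, FAS, and the Non-e4/e4 Set, respectively". No ARIA, AESI or AE table by assigned arm is planned.

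**The concern.** Receiving 15 mg/kg at Dose 1 is the correct start of the 60 mg/kg regimen, not a dispensing error. Yet a 60 mg/kg participant whose pre-Dose 2 scan shows ARIA is tabulated at 15 mg/kg. One with the same exposure and a clean scan goes on to be tabulated at 60 mg/kg. Group membership thus depends on the outcome being counted.

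The curves and early visits show it most clearly. In SAP Table 7-9 the Week 2, 4 and 6 MRI windows end by Day 50, while 60 mg/kg is due on Day 57. A titrated participant managed under current Table 7 can enter the 60 mg/kg column only if no ARIA was found earlier, so that column carries guaranteed ARIA-free time.

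This is a dose-ranging study. Protocol 1.4 expects it to inform the Phase 3 dose, and ARIA is both an AESI and an identified risk. These displays are the ones planned for reading ARIA across doses.

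**Working it through.** **Rule trace** (SAP 5.2 and Table 3-1, protocol Table 7; titrated participants, current restart rule)

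| Randomised | ARIA found after Dose 1 | after Dose 2 | after Dose 3 |
|---|---|---|---|
| 60 mg/kg | counted at 15 | counted at 40 | counted at 60 |
| 40 mg/kg | counted at 15 | counted at 40 | counted at 40 |
| 15 mg/kg | counted at 15 | counted at 15 | counted at 15 |

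**Denominator.** The plan's own size reproduces: 4 × 70 + 15 + 6 + 27 = 328, and 328/4 = 82. Removing the 15 e4 homozygotes and the 6 never dosed gives (328 − 15 − 6)/4 = 76.75, about 77 per arm. The rates below do not depend on this number.

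**Assumed inputs (none is in the documents).**
- True ARIA of 10/20/25% at 15/40/60 mg/kg.
- *a* = ARIA found after Dose 1 and *b* = after Dose 2, in the ratio 5:8 and equal in the 40 and 60 mg/kg arms, which are treated alike through Dose 2.
- *s* = share of 60 mg/kg ARIA found before Dose 3, so a + b = 25% × s.
- *m* = titrated share × share of titration-phase ARIA cases that did not resume titration.

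**Tabulated rates.**
- 15 mg/kg: (0.10 + 2ma)/(1 + 2ma)
- 40 mg/kg: (0.20 − ma + mb)/(1 − ma + mb)
- 60 mg/kg: (0.25 − m(a+b))/(1 − m(a+b))
- Combined 40+60: (0.45 − 2ma)/(2 − 2ma)

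For s = 26% (a = 2.5%, b = 4%) and m = 1, with 77 per arm: 11.55/80.85 = 14.3%, 16.55/78.16 = 21.2% and 14.24/72.00 = 19.8%.

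For s = 52% (a = 5%, b = 8%) and m = 1: 15.40/84.70 = 18.2%, 17.71/79.31 = 22.3% and 9.24/66.99 = 13.8%.

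| s | m | 15 / 40 / 60 mg/kg | Combined 40+60 |
|---|---|---|---|
| true rates | – | 10 / 20 / 25% | 22.5% |
| 26% | 1 | 14.3 / 21.2 / 19.8% | 20.5% |
| 26% | 0.25 | 11.1 / 20.3 / 23.8% | 22.0% |
| 52% | 1 | 18.2 / 22.3 / 13.8% | 18.4% |
| 52% | 0.25 | 12.2 / 20.6 / 22.5% | 21.5% |

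Total AL002 stays at (10 + 20 + 25)/3 = 18.3%, because moves are only between AL002 columns.

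**A second set of assumptions.** Take a flat 20% in every arm, 2% found before each of Doses 2 and 3, and all such cases moving. Then 0.24/1.04 = 23.1%, 0.20/1.00 = 20.0% and 0.16/0.96 = 16.7%. A flat truth shows as a falling dose trend.

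**When would 60 mg/kg fall below 15 mg/kg?** Set the first and third formulas equal, with x = m(a+b) and 2ma = (10/13)x. This gives 0.15 = 1.477x, so x = 0.1016 and s = 0.406/m. The threshold is 41% at m = 1 and 54% at m = 0.75. Because the two higher arms are treated alike through Dose 2, a + b cannot exceed the 40 mg/kg arm's 20% total, so s is at most 20/25 = 80%. Reversal is therefore impossible for m below 0.406/0.80, about 0.51.

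**Condition on direction.** Stops for reasons other than ARIA during titration also move people down. At a 25% rate, 60 mg/kg is understated if those moved out number fewer than 3 per ARIA case moved out (0.75/0.25). At a 10% rate, 15 mg/kg is inflated if those moved in number fewer than 9 per ARIA case (0.90/0.10). Adding 2.5% such stops after each of Doses 1 and 2 (s = 26%, m = 1) gives 13.6/21.2/20.9%.

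**The case against.** The best defence is that the grouping is deliberate and follows the protocol. Protocol 8.3.4 assigns safety participants by treatment actually received, and SAP 5.2 addresses titration expressly. Someone who only ever received 15 mg/kg was not exposed to 60 mg/kg, and an assigned-arm table charges the event to a dose not given. That stands as a reason to keep the as-treated display. It does not make the ARIA rates comparable across columns. Counting an event at the dose held at onset needs matching exposure below the line, and event-free 40 and 60 mg/kg participants who passed through 15 mg/kg are not counted there.

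The effect may also be small. At s = 26% and m = 0.25, about 1.3 participants leave the 60 mg/kg column and the ordering survives. This is right, and the documents cannot settle it.

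There is partial mitigation. Listings are sorted by randomised and then actual treatment, so a reader could recount ARIA by arm. The planned tables and curves would remain uncorrected.

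A reader might go further and infer that all AE tables are biased in a known direction. The documents do not support that. Treatment-emergent events count only if they start "no later than 90 days after the last dose date", so a participant stopped after one dose is observed to Day 91 (1 + 90), or to Day 119 (29 + 90) after two. A full course runs to Day 427 (337 + 90) or Day 763 (673 + 90). A participant moved down may bring few other events, so the net direction is open.

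**Conclusion.** The point holds for ARIA and ARIA-driven AESI by dose, including the by-visit tables and the Kaplan-Meier curves. It affects titrated participants managed under current Table 7. Untitrated participants do not move, nor do any who resumed titration under an earlier restart rule (duration unknown).

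The tendency is inflation at 15 mg/kg, understatement at 60 mg/kg and partial understatement in the combined 40+60 group, provided non-ARIA titration stops do not greatly outnumber the ARIA cases moved. The 40 mg/kg column both loses and gains cases. If no ARIA is found before the target dose, no ARIA case moves.

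The mechanism is certain from the rules, but its size is not known. A reader might infer that the tables will show 60 mg/kg as safer than 15 mg/kg. Under the assumptions above, that needs a large early share and m of at least about 0.51, and nothing in the documents shows either. Nor does the SAP contradict protocol 8.3.4. What is missing is an ARIA comparison whose groups do not depend on ARIA. This should be fixed before the ARIA results are read by dose.

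**What to change.** In the SAP:

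1. Add ARIA-E, ARIA-H and AESI incidence tables and the ARIA Kaplan-Meier curves for the Non-e4/e4 Set by randomised regimen, and name these as the basis for comparing ARIA across doses.
2. Add a descriptive table of ARIA by dose at onset, with exposure time at that dose as the denominator.
3. Keep the highest-dose-received tables as the as-treated display under protocol 8.3.4, including for general AEs and PK. Footnote them to say that early ARIA can move a participant to a lower dose group.
4. Record this in SAP Section 9, which does not mention the grouping rule.

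The cost is a few extra tables and curves. The assigned-regimen tables will count some events under a target dose not yet reached, and the dose-at-onset table makes that visible. No data collection, conduct or dosing rule changes.

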#### 5.3 Analysis Sets Excluding APOE e4-homozygous (e4/e4) Participants

The AL002-2 study originally included enrollment of participants who were APOE e4 homozygotes (e4/e4). However, further enrollment of participants with this APOE genotype was permanently stopped after the evaluation of safety among the early enrolled participants with e4/e4. Therefore, the primary objective of the study changed to the assessment of AL002 in the participants without e4/e4.

As a result, all analyses will primarily be based on all participants who were randomized, received any study treatment, and are not e4/e4 (non-e4/e4), unless otherwise specified. A limited set of analyses will be provided for the e4/e4 participants as specified in the SAP.

A participant's APOE e4 status and APOE genotype will be determined by the APOE genotype central laboratory data provided by the vendor. If a participant's APOE genotype is not e4/e4, then the participant is not APOE e4-homozygous (i.e., the participant is non-e4/e4).

#### 5.3.1 Full Analysis Set (FAS)

The FAS will consist of all participants who were randomized, received any amount of study drug, and are non-e4/e4. All analyses using the FAS will group participants according to the assigned treatment.

When change (or percent change) from baseline is assessed based on the FAS, participants will be included in the analysis only if the participants had both a baseline and a postbaseline measure.

#### 5.3.2 Per-Protocol Analysis Set (PPS)

The PPS will consist of all participants in the FAS excluding participants who met either criterion:

- Any participant who did not receive at least 3 doses of study drug (i.e., total doses of study drug < 3),

- Any participant with major protocol deviations due to inclusion/exclusion criteria.

Protocol No. AL002-2 Last Revision Date: 12 Aug 2025

All analyses using the PPS will group participants according to the assigned treatment. This analysis set will be used for supplementary analyses of the primary efficacy endpoint.

#### 5.3.3 Non-e4/e4 Set

The Non-e4/e4 Set will consist of all participants who received any study treatment and are non-e4/e4.

All analyses using the Non-e4/e4 Set will group participants according to the actual treatment received and follow the same rules as described above in the ATS (Section 5.2).

#### 5.3.4 Pharmacokinetic (PK) Set

The PK Set will include all participants in the ATS that received AL002, had at least one post-dose measurable concentration, and are non-e4/e4. The PK Set will only be used for concentration descriptive summary.

All PK summaries using the PK Set will group participants according to the actual treatment received and follow the same rules as described above in the ATS (Section 5.2).

### 5.4 APOE e4-Homozygous Participants Set (e4/e4 Set)

The e4/e4 Set will consist of all randomized and dosed participants who are e4/e4. In other words, this subset includes e4/e4 dosed participants.

Analyses for this subset will group participants according to the actual treatment received and follow the same rules as described above in the ATS (Section 5.2).

Protocol No. AL002-2 Last Revision Date: 12 Aug 2025

#### 6. SPECIFICATION OF ENDPOINTS AND VARIABLES

#### 6.1 Demographics and Baseline Characteristics

In general, baseline will be defined as the last non-missing assessment, including repeated and unscheduled assessments, prior to the first study treatment administration, unless otherwise specified. If the date of an assessment is on the day of the first study treatment administration and the *chronological* order of the first study treatment administration and the assessment is indeterminate (e.g., because the specific time of the assessment is unknown), the assessment will be used as the baseline, unless otherwise specified. Selection of baseline is specified in Section 7.1.2.

#### **6.1.1** Demographics and Baseline Characteristics

Demographic information, including year of birth, age at time of informed consent (in years), sex, race, ethnicity and handedness will be collected at the Screening visit.

Weight and height will be collected at the Screening visit. Weight will be collected throughout study. Body mass index (BMI) will be calculated as the weight in kg divided by the square of height in meters.

Social history will be collected in the Screening visit. It includes the following information, past and current, regarding the participant: educational attainment, marital status, employment status, tobacco use (smoking, vaping, chewing), alcohol consumption, cannabinoid use and recreational drug use.

Age at AD diagnosis will be calculated from the date of diagnosis and birth year as {(year of diagnosis) – (year of birth)}.

Time since AD diagnosis will be calculated from the date of diagnosis and informed consent date as {(informed consent date) – (AD diagnosis date) / 365.25}. If AD diagnosis date is partially missing, unknown day will be imputed as the 1st, and unknown month will be imputed as January.

The countries where a participant is enrolled will be grouped into geographical region, namely, United States and rest of the world.

A participant's APOE e4 status and APOE genotype will be determined by the APOE genotype central laboratory data provided by the vendor. If a participant's APOE genotype contains "e4", the participant is considered an e4 carrier (or carrier); otherwise, a non-e4 carrier (or non-carrier).

The PD biomarker assessments will consist of, but are not limited to, blood-based biomarkers, CSF-based biomarkers (when available), and imaging biomarkers and will be collected during screening. Other timing and frequency of all PD biomarker assessments are presented in the Schedules of Assessments in protocol.

Protocol No. AL002-2 Last Revision Date: 12 Aug 2025

#### **Demographic variables will include the following:**

- Age (years) as a continuous variable and as categories
  - o Age group 1
    - < 65 years

    - $\geq$  65 years
    - Missing (including blank, not reported, unknown, etc.)
  - o Age group 2
    - < 65 years
    - $\geq$  65 < 75 years
    - $\geq 75$  years
    - Missing (including blank, not reported, unknown, etc.)
- Sex
  - o Female
  - o Male
  - Missing (including blank, not reported, unknown, etc.)
- Race
  - o American Indian or Alaska Native
  - o Asian
  - o Black or African American
  - o Native Hawaiian or Other Pacific Islander
  - o White
  - o Multiple
  - o Missing (including blank, not reported, unknown, etc.)
- Ethnicity
  - o Hispanic or Latino
  - Not Hispanic or Latino
  - o Missing (including blank, not reported, unknown, etc.)
- Handedness
  - o Always Right
  - o Usually Right
  - o Either Hand
  - o Usually Left
  - o Always Left
  - o Missing (including blank, not reported, unknown, etc.)
- Weight (kg)
- Height (cm)
- BMI (kg/m2) as a continuous variable and as categories
  - $\circ$  < 18.5 kg/m^2
  - $\circ$  18.5  $< 25.0 \text{ kg/m}^2$
  - $\circ$  25.0 < 30.0 kg/m^2
  - $\circ \quad \geq 30.0 \; kg/m^2$
- Geographical region
  - United States
  - o Rest of World

Protocol No. AL002-2 Last Revision Date: 12 Aug 2025

